9 STUDY PROCEDURES

Table 1 outlines the timing of assessments to be performed throughout the study. See Sections 10 and 11 for additional details of study procedures.

Table 1 Schedule of Assessments

Period	Screening Visit	Treatment Period					Final Visit (End of Treatment) ^a
		Baseline Visit	Week 2	Week 3	Week 4	Week 5	
Week	Week 0	Week 1 (1 week ±1 day after screening)	Week 2 (±1 day)	Week 3 (±1 day)	Week 4 (±1 day)	Week 5 (±1 day)	Week 5 (±1 day)
Visit	1	2	3	At home	At home	4	
Informed Consent	X						
Demographics	X						
Inclusion/Exclusion Criteria	X	X					
Medical History/ Wound History	X	X					
Concomitant Medication Review	X	X	X		X		X
Vital Signs ^b	X						X
Physical Examination	X						
Brief Physical Examination							X
Collect Blood for Clinical Laboratory Tests	X ^c						X
Wound-QoL Questionnaire ^d	X	X	X		X		X
Wound Assessment ^e	X	X	X				X
Measure Wound(s) Size Using Study Rulers	X	X ^f	X ^f				X ^f
Photograph Wound(s) Using Study Camera		X ^f	X ^f				X ^f
Dispense Diary ^g		X	X				
Collect/Review Diary			X				X
Administer Study Treatment ^h		X	X		X		X
Provide/Review Instructions on Treatment and Diary ^g		X	X				
Dispense Study Treatment ^g		X	X				
Perform Study Treatment Accountability			X				X

Period	Screening Visit	Treatment Period					Final Visit (End of Treatment) ^a
		Baseline Visit	Week 2 (±1 day)	Week 3 (±1 day)	Week 4 (±1 day)	Week 5 (±1 day)	
Week	Week 0	Week 1 (1 week ±1 day after screening)	Week 2 (±1 day)	Week 3 (±1 day)	Week 4 (±1 day)	Week 5 (±1 day)	Week 5 (±1 day)
Visit	1	2	3	At home	At home	4	4
Adverse Event Assessment ^f		X	X	X	X	X	X

Abbreviations: AE=adverse event; IFU=Instructions for Use; Wound-QoL=Wound Quality of Life

^aOr early discontinuation visit.

^bVital sign measurements will be performed at screening and at the Week 5 (end of treatment or early discontinuation) visit.

^cAt screening, clinical laboratory tests will be done only if results from tests performed within 1 month prior to screening are not available. Tests include standard hematology and serum chemistry, plus glycated hemoglobin.

^dPatients must complete the Wound-QoL questionnaire before any other study-related procedure, including any dressing change (with the exception of consenting the patient at screening). Patients will be given several blank Wound-QoL questionnaires at the Week 2 visit to fill out on specific dates during Weeks 3 and 4 (on the same day each week); study site personnel will call the patient on these dates to remind them to fill out the questionnaires prior to study treatment on those dates.

^eThe Investigator or designee will assess the wound(s) for appearance, granulation tissue, exudate, drainage, surrounding erythema and/or swelling, and any signs of infection.

^fTo be done pre-cleaning and post-cleaning.

^gA diary and sufficient study treatment to use until the next visit will be dispensed to patients. Instructions on administering study treatment, recording treatment dates and times and any reactions to treatment in the diary will be explained to the patient and/or caregiver.

^hProntosan solution and Prontosan gel will be administered by the Investigator or designee at each clinic visit. At home, patients or their caregivers will administer Prontosan solution and Prontosan gel. Each patient's treatment regimen will be given per the institutional guidelines and the Prontosan IFU.

ⁱAt home, AEs are collected in the patient diary. In the clinic, patients are assessed for AEs by the Investigator.

9.1 Patient Informed Consent

The Investigator or designee will explain the nature of the study, the study procedures, and the potential risks to each patient. Before any study-related procedures occur, the patient must voluntarily sign the ICF.

9.2 Procedures by Study Week

Assessments are to be performed as outlined in the following by-week subsections. If the patient has 2 wounds, both wounds will be treated with the Prontosan Solution and Prontosan Gel and other study specific procedures will be performed on both wounds.

9.2.1 Week 0 (Screening)

The following assessments will be performed by the Investigator or designee at the screening visit (Week 0, Visit 1):

- Obtain informed consent.
- After the patient gives consent, ask the patient to complete the Wound-QoL questionnaire before any other visit assessment.
- Obtain demographic data.
- Collect medical history and wound history (including wound type, wound age, location, past complications, and current dressing change frequency) for both wounds if 2 are present.
- Record prior and concomitant medications for the wound(s) and other indications.
- Measure vital signs (blood pressure, pulse, temperature) and weight and height.
- Perform a physical examination.
- Assess the wound(s) appearance, granulation tissue, exudate, drainage, surrounding erythema and/or swelling, and any signs of infection.
- Measure the wound(s) size with a standard, single-use, disposable ruler using the clock method (see Section 10.3 and Section 15, Appendix 2).
- Collect blood for measuring HbA1c and for standard hematology and serum chemistry parameters if the results are not available for tests done within 1 month prior to screening.
- Review the inclusion/exclusion criteria to assess eligibility.

Patients who meet all of the inclusion criteria and none of the exclusion criteria will be eligible to enter the study and will be assigned a patient number. Eligibility will be confirmed at the Week 1 visit (Baseline, Visit 2) which will occur 1 week \pm 1 day after the Screening visit.

9.2.2 Week 1 (Baseline)

The Week 1 visit (baseline visit) will occur 1 week \pm 1 day following the screening visit.

At the Week 1 visit, the following assessments will be performed by the Investigator or designee:

- Ask the patient to complete the Wound-QoL questionnaire before any other visit assessment.
- Confirm patient eligibility.
- Confirm medical and wound histories.
- Record concomitant medications.
- Assess the wound(s) appearance, granulation tissue, exudate, drainage, surrounding erythema and/or swelling, and any signs of infection.
- Measure the wound(s) size pre-treatment (pre-debridement) with a standard, single-use, disposable ruler using the clock method (see Section 10.3 and Section 15, Appendix 2).
- Photograph the wound(s) pre-treatment (pre-debridement) using the study camera and a standard, single-use, disposable ruler to indicate relative size.
- Clean the wound(s) and wound area(s) with Prontosan solution per the institutional guidelines and the Prontosan IFU for the individual patient wound(s).
- Assess the patient for any AEs.
- Measure the wound(s) size post-cleaning (post-debridement) with a standard, single-use, disposable ruler using the clock method.
- Photograph the wound(s) post-cleaning (post-debridement) using the study camera and a standard, single-use, disposable ruler to indicate relative size.
- Apply Prontosan gel to the wound(s) and apply the bandage/dressing per the institutional guidelines and the Prontosan IFU for the individual patient wound(s).
- Dispense enough study treatment to the patient to last until the next study visit.
- Provide training to the patient (and/or the caregiver) on administering the study treatment at home.
- Instruct the patient (and/or the caregiver) to record the liquid level remaining after each use, and to return all used bottles and any unused bottles of study treatment at the next visit for product accountability.
- Dispense a diary to the patient and provide training to the patient (and/or the caregiver) to record the date and time of each treatment and any reactions to treatment. Remind the patient to bring the diary to the next visit.

9.2.3 Week 2

At the Week 2 visit, the following assessments will be performed by the Investigator or designee:

- Ask the patient to complete the Wound-QoL questionnaire before any other visit assessment.
- Review the diary and examine used bottles and any unused bottles of study treatment.
- Record concomitant medications.
- Assess the wound(s) appearance, granulation tissue, exudate, drainage, surrounding erythema and/or swelling, and any signs of infection.

- Measure the wound(s) size pre-treatment (pre-debridement) with a standard, single-use, disposable ruler using the clock method (see Section 10.3 and Section 15, Appendix 2).
- Photograph the wound(s) pre-treatment (pre-debridement) using the study camera and a standard, single-use, disposable ruler to indicate relative size.
- Clean the wound(s) and wound area(s) with Prontosan solution per the institutional guidelines and the Prontosan IFU for the individual patient wound(s).
- Assess the patient for any AEs.
- Measure the wound(s) size post-cleaning (post-debridement) with a standard, single-use, disposable ruler using the clock method.
- Photograph the wound(s) post-cleaning (post-debridement) using the study camera and a standard, single-use, disposable ruler to indicate relative size.
- Apply Prontosan gel to the wound(s) and apply the bandage/dressing per the institutional guidelines and the Prontosan IFU for the individual patient wound(s).
- Dispense enough study treatment to the patient to last until the next study visit.
- Provide training to the patient (and/or the caregiver) on administering the study treatment at home.
- Instruct the patient (and/or the caregiver) to record the liquid level remaining after each use, and to return all used bottles and any unused bottles of study treatment at the next visit for product accountability.
- Dispense a new diary to the patient and provide training to the patient (and/or the caregiver) to record the date and time of each treatment and any reactions to treatment. Remind the patient to bring the diary to the next visit.
- Provide several blank Wound-QoL questionnaires to the patient and ask the patient to complete one of them on a specific date during Week 3 and another on a specific date during Week 4 (on the same day each week).

9.2.4 Weeks 3 and 4

During Weeks 3 and 4, patients will either self-administer study treatment or be treated by their caregiver (as trained by the Investigator or designee). Frequency of administration will vary by patient per the regimen provided by the Investigator or designee.

On dates specified by the study site (one during Week 3 and one during Week 4, on the same day each week), patients will complete the Wound-QoL questionnaire prior to any study treatments on those days. Site personnel will call patients to remind them to complete the questionnaires and to reinforce completing the diary at each treatment. Site personnel will also ask about any concomitant medication changes.

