	
[PHMB]), and sodium hydroxide for pH adjustment. In this study, the 350-mL squeeze bottle will be used.
 
Prontosan Wound Gel is a clear, colorless gel containing glycerol, hydroxyethylcellulose, 0.1% undecylenamidopropyl betaine, 0.1% PHMB, and purified water; it is packaged in a 30-mL squeeze bottle.
 
The frequency and method of Prontosan solution and Prontosan gel applications will be per the institutional guidelines and the Prontosan IFU for the individual patient wound(s).

Reference Device:	Not applicable
Treatment Duration:	Each patient will receive 4 weeks of study treatment.
Criteria for Evaluation:	
Patient QoL will be evaluated from the global score and the subscores (Body, Psyche, Everyday Life) of the Wound-QoL questionnaire to be assessed at Week 0 (screening visit) for eligibility, and at Weeks 1 (baseline visit), 2, 3, 4, and 5 (end of treatment or early discontinuation visit). Wound size(s) will be measured with standard, single-use, disposable rulers at Week 0 (screening visit) for eligibility; and measured with standard, single-use, disposable rulers and documented with digital photography before and after study treatment at Weeks 1 (baseline visit), 2, and 5. At screening, the Investigator will assess wound history for the wound(s) (wound type, wound age, location, past complications, and current dressing change frequency). At all visits, the Investigator will assess the wound(s) appearance, granulation tissue, exudate, drainage, surrounding erythema and/or swelling, and any signs of infection.
 
Safety will be evaluated from AEs, ADEs, and physical examinations.

Study Endpoints:
	
Primary Endpoint
 
 • Change from baseline to Week 5 in the global score of the Wound-QoL questionnaire 
Secondary Endpoints
 
 • Change from baseline to Week 5 in the Body subscore of the Wound-QoL questionnaire • Change from baseline to Week 5 in the Psyche subscore of the Wound-QoL questionnaire • Change from baseline to Week 5 in the Everyday Life subscore of the Wound-QoL questionnaire 
Exploratory Endpoint
 
 • Change from baseline to Week 5 in the appearance and size of the wound(s)

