At the Week 2 visit, the following assessments will be performed for the wound(s) at the clinic: the Wound-QoL questionnaire (to be completed before any other procedure), patient diary review, product accountability review, concomitant medication review, wound assessment, wound size measurement and photography of the wound prior to and after cleaning/debridement, and AE review. The wound(s) will be treated with Prontosan solution and Prontosan gel by the Investigator or designee per the institutional guidelines and the Prontosan IFU. Bottles of Prontosan solution and Prontosan gel will be dispensed in sufficient quantity for the patient's treatment regimen until the next clinic visit (Week 5). The patient (and/or the caregiver) will receive instructions on how to continue study procedures at home during Weeks 3 and 4. The patient will be given a new diary and retrained to record the date and time of each treatment and any reactions to treatment in the diary. Patients (and/or caregivers) will also be reinstructed to record the liquid level remaining after each use, and to return all used bottles and any unused bottles of study treatment at the next visit for product accountability. Wound-QoL questionnaires will be provided for patients, and instructions will be provided about completing the questionnaires at home during Weeks 3 and 4 on specific dates (on the same day each week).

Weeks 3 and 4

At Weeks 3 and 4, there are no scheduled study related clinic visits. Patients will continue Prontosan treatment at home according to the study doctor's instructions and according to the training received at the Week 2 visit. The study site will call the patients to remind them to complete the Wound-QoL questionnaires on specific dates (on the same day each week) and that on these dates, the Wound-QoL questionnaire must be completed prior to study treatment or other study procedures. Once during each week, the study site will also inquire about any changes or additions to a patient's concomitant medications.

Week 5 (End of Treatment or Early Discontinuation) Visit

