8.4.2 Prior and Concomitant Medications

Any medication or therapy that is taken by or administered to the patient during the course of the study must be recorded in the eCRF. Prior medications are defined as those taken by or administered to the patient before screening and up to the first study treatment. Concomitant medications are defined as those taken by or administered to the patient after the first study treatment. After the first treatment, medication to treat minor treatment-emergent illness is generally permitted; however, the following therapies are expressly prohibited throughout the study:

- Any antibiotic therapy for treatment of the wound. Antibiotic therapy for treatment of infections not related to the wound are acceptable.
- Oral, or parenteral corticosteroids, immunosuppressive agents, or cytotoxic agents (see Exclusion Criteria #7 for exceptions)
- Any investigational drug or device
- Any additional wound treatment topical solutions, including medicated dressings

At screening, if a patient has a wound infection that is being treated with one of these prohibited medications, the patient may be scheduled for a re-screening after the infection in the wound has cleared. At the re-screening, the patient must still meet all inclusion criteria and not exhibit any exclusion criteria, and the appropriate washout time for antibiotics (7 days) and/or for corticosteroids, immunosuppressive agents, and cytotoxic agents (30 days) must have been met prior to the first study treatment.

During the study, if a patient develops an infection in the wound(s) and requires treatment with a prohibited medication, the patient will be discontinued from the study. Patients who withdraw or are withdrawn before completion of the Week 2 assessments and the Week 3 Wound-QoL questionnaire will be replaced to ensure that at least 52 patients will complete the study.

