11.4 Adverse Events

11.4.1 Adverse Events

An AE is any symptom, physical sign, syndrome, or disease that either emerges during the study or, if present at screening, worsens during the study, regardless of the suspected cause of the event. All medical and psychiatric conditions (except those related to the indication under study) present at screening will be documented in the medical history eCRF. Changes in these conditions and new symptoms, physical signs, syndromes, or diseases should be noted on the AE eCRF during the rest of the study. Clinically significant laboratory abnormalities should also be recorded as AEs.

Adverse device effects (ADEs) are defined as AEs that are considered related to the study device. Possible anticipated ADEs with Prontosan solution or Prontosan gel include burning sensation, itching, and rash. In rare cases (1:10,000), anaphylactic shock has been reported after use of Prontosan solution or Prontosan gel.^{9,10}

Patients and/or caregivers will be instructed to report AEs in the diary, and patients will be monitored for AEs at each study visit. All AEs are to be followed until resolution or until a stable clinical endpoint is reached.

Each AE is to be documented in the eCRF with reference to start and stop dates, frequency, severity, relationship to study device (related: yes or no), action taken with study device, treatment of event, and outcome. Furthermore, each AE and each ADE are to be classified as being serious or non-serious. Changes in AEs and AE resolution dates are to be documented in the eCRF.

For the purposes of this study, the period of observation for collection of AEs extends from the time the patient gives informed consent until the final visit. Follow-up of an AE, even

after the end of treatment, is required until the event resolves or stabilizes at a level acceptable to the Investigator.

Specific guidelines for classifying AEs by intensity are given in Table 3.

Table 3 Classification of Adverse Events by Intensity

Mild: An event that is easily tolerated by the patient, causing minimal discomfort and not interfering with everyday activities.
Moderate: An event that is sufficiently discomforting to interfere with normal everyday activities.
Severe: An event that prevents normal everyday activities.

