11.4.3 Serious Adverse Event Reporting

An SAE occurring during the study must be reported to the Sponsor or designee (details for reporting will be in the Safety Plan and on the SAE form). Any such SAE due to any cause, whether or not related to the study device, must be reported within 24 hours of occurrence or when the Investigator becomes aware of the event. Notification can be made with the SAE reporting form as described in the following paragraphs:

1. Contact the study safety team to inform them that you are faxing an SAE form. The study safety team is available 24 hours a day, 7 days a week. If you are unable to speak with a live safety associate, leave a message with the name of the Investigator, your name, the telephone number where you can be reached, and the protocol number and title.
2. Fax the SAE form and any supporting documentation to the study safety team within 24 hours of becoming aware of the event. Verify successful transmission by

obtaining a Fax Confirmation Report; this confirmation page should be kept with the SAE report in case future monitoring is required.

The event must also be recorded on the AE eCRF. Preliminary reports of SAEs must be followed by detailed descriptions later on, including clear and anonymized photocopies of hospital case reports, consultant reports, autopsy reports, and other documents when requested and applicable. SAE reports must be made whether or not the Investigator considers the event to be related to the study device.

Appropriate remedial measures should be taken to treat the SAE, and the response should be recorded. Clinical, laboratory, and diagnostic measures should be employed as needed in order to determine the etiology of the problem. The Investigator must report all additional follow-up evaluations to the Sponsor Study Physician within 10 calendar days. All SAEs will be followed until the Investigator and Sponsor agree the event is satisfactorily resolved. The Sponsor will report SAEs to the FDA.

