3. STUDY DESIGN

This is a prospective, open-label, multi-site, single-arm study in patients with chronic leg wound(s). The investigator or designee will apply Prontosan solution and Prontosan gel to the wound(s) at clinical visits Week 1, Week 2, Week 5. Patients will apply Prontosan solution and Prontosan gel themselves (or have them applied by a caregiver) at home (Week 3 and Week 4). The study contains Screening period (Week 0), 4 weeks of treatment period (Week 1 – Week 5), and safety follow-up.

The schedule of assessments to be performed throughout the study is given in the protocol.

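### Between the Week 2 and Week 5 visits (about 21 of 28 treatment days) the site has no scheduled adverse event enquiry, and the diary training is narrower than the AE definition

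*Protocol*

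**What the plan says.** **Contacts.** SAP section 3 places treatment by the site at "clinical visits Week 1, Week 2, Week 5". Protocol 6.1 states: "At Weeks 3 and 4, there are no scheduled study related clinic visits".

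**Calls.** The synopsis and 6.1 describe calls in Weeks 3 and 4 that remind patients about the questionnaire and check for medication changes. Section 9.2.4 adds encouragement to fill in the diary and ends: "Site personnel will also ask about any concomitant medication changes". None of the three places lists a question on AEs, product reactions or wound infection.

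**AE assessment at home.** Table 1 marks AE assessment at Weeks 3 and 4. Its footnote i explains that AEs at home are collected in the patient diary. After the new diary is handed out at Week 2, Table 1 and 9.2.5 schedule its review at Week 5. Signs of infection are assessed by the site at clinic visits (10.2).

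**Diary content.** In 9.2.2 and 9.2.3 the aim of the diary instruction reads: "to record the date and time of each treatment and any reactions to treatment. Remind the patient to bring the diary to the next visit". The synopsis, 6.1, 8.2 and Table 1 footnote g give the same scope. Section 11.4.1 defines an AE whatever its suspected cause and says: "Patients and/or caregivers will be instructed to report AEs in the diary, and patients will be monitored for AEs at each study visit".

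**Provisions that respond to events.** An SAE "must be reported within 24 hours of occurrence or when the Investigator becomes aware of the event" (11.4.3). Under 8.4.2, "if a patient develops an infection in the wound(s) and requires treatment with a prohibited medication, the patient will be discontinued from the study". Section 9.2.6 allows unscheduled visits for AEs.

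**The concern.** The site already speaks to each patient in both home weeks, yet the calls as specified leave out the one safety question that would be natural to ask. From Week 2 to Week 5 the site learns of an event only if the patient volunteers it or if the event leads to a medication that comes up on the call.

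Two things are at stake. The first is timing. SAE reporting, unscheduled visits and the infection provision all depend in practice on someone at the site knowing of the event. A rash or an untreated infection soon after Week 2 could stay unknown for up to about three weeks while home treatment continues.

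The second is completeness. Section 11.4.1 requires start and stop dates, severity and relatedness for each AE, and asks for separate onset dates when intensity changes over days. A patient trained to write down reactions to the product has no clear reason to write down a fall or an illness that seems unconnected with it. Such events then depend on recall at Week 5, and the patient's own view of causality filters them before the Investigator judges relatedness.

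**Working it through.** **Inputs**
- Treatment duration: "Each patient will receive 4 weeks of study treatment" (synopsis), taken as 28 days.
- Clinic visits during treatment: Weeks 1, 2 and 5 (SAP section 3; Table 1).
- Windows: ±1 day for Weeks 2 to 5 (Table 1; SAP 5.1.4).
- Calls: one in each of Weeks 3 and 4, on the questionnaire dates (Table 1 footnote d).

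**Stated duration reproduced.** Week 5 − Week 1 = 4 weeks = 28 days, as the synopsis says. Call the baseline visit day 0. Week 2 is then day 7 and Week 5 is day 28.

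**Interval with no scheduled AE enquiry by the site**
- Nominal: 28 − 7 = 21 days, and 21/28 = 75% of treatment.
- Shortest: Week 2 a day late (day 8) and Week 5 a day early (day 27), so 27 − 8 = 19 days, and 19/27 = 70%.
- Longest: Week 2 a day early (day 6) and Week 5 a day late (day 29), so 29 − 6 = 23 days, and 23/29 = 79%.

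**With an AE question in both calls.** Calls near days 14 and 21 give contacts at days 7, 14, 21 and 28. The longest nominal gap is 7 days, and 7/28 = 25%. If the two ends of a gap shift by a day in opposite directions, it is at most 7 + 2 = 9 days.

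**Diary wording side by side**

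| Place | What the patient is to record |
|---|---|
| Synopsis, 6.1, 8.2, 9.2.2, 9.2.3, footnote g | Treatment dates and times, and reactions to the treatment |
| 11.4.1 | AEs, whatever the suspected cause |
| Footnote i | AEs at home |

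The first row holds the instructions that site staff carry out with the patient. The other two state what the diary is meant to deliver. An event that the patient does not link to the product falls within the second and third rows but outside the first.

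**The case against.** Much of the opposing case stands.

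- **The diary is meant for AEs.** Section 11.4.1 and footnote i say so, and the diary form itself is not in the documents. A reader might infer that patients are told to record reactions only. What can be shown is an inconsistency between the training steps and the AE section.
- **AEs in the interval are asked about.** At Week 5 the site reviews the diary, assesses AEs without restriction and inspects the wound (9.2.5). A reader might infer that nobody ever asks about three-quarters of treatment. That is wrong: the enquiry is late, not missing.
- **The safety rules are not disabled.** A reader might infer that they cannot work. The 24-hour rule allows for later awareness, and 11.4.3 refers to a Safety Plan that is not available here. The infection provision is triggered by a prohibited medication, and both calls ask about medication changes, so a wound antibiotic already started may come to light. An infection not yet treated, or an AE needing no medication, would not.
- **The reported device-effect percentage is not inflated.** A reader might infer that missing unrelated AEs raises it. SAP 5.2.6 uses the number of patients in the safety population as the denominator, so it does not. Missed unrelated, non-serious events would affect the count of patients with at least one TEAE and the listings.
- **No infection count can be given.** The background section reports 29 of 953 patients (3%) with a first or renewed wound infection. It is tempting to apply this to 52 patients, but no follow-up time per patient is stated, so it cannot be turned into a 4-week rate.

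It is also fair that this is a Phase 4 study of commercially available products with no safety objective. That limits the weight of the point. It does not explain leaving the question out of calls that are already planned.

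**Conclusion.** The point holds as one of prompt capture and consistent wording. Between Weeks 2 and 5 the plan schedules no AE enquiry by the site for about 21 of 28 treatment days (19 to 23 days; 70% to 79%). Capture at home relies on a diary that is not reviewed until Week 5, and its training text is narrower than 11.4.1. The consequences are delayed site awareness and recall of up to about three weeks. Some under-recording of events that patients do not attribute to the product is plausible, but the documents give no basis for estimating how much.

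This rests on two assumptions: that the calls contain what the protocol lists and nothing more, and that the diary form follows the training text. If the form or the Safety Plan already prompts for all AEs, the wording issue shrinks to a protocol correction. The primary QoL analysis is not affected.

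**What to change.** 1. **Calls.** In 9.2.4, 6.1, the synopsis and Table 1 footnote i, add a question on AEs to the Week 3 and Week 4 calls. It should cover reactions to the products and signs of wound infection. Enter the answers in the eCRF and report any SAE under 11.4.3.
2. **Diary.** Reconcile the training wording in the synopsis, 6.1, 8.2, 9.2.2, 9.2.3 and footnote g with 11.4.1, so that patients record any new or worsening symptom or health event. Check that the diary form matches.

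No treatment or discontinuation rule needs to change. The cost is slightly longer calls, an edit to the diary wording and a few more AEs to enter. No new visits or staff are needed.
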